[11]	STATISTICAL EVALUATION	15

The efficacy of stabilized chlorine dioxide rinse as a chemical adjuvant for treatment of Peri-Implant Mucositis.

[1] Introduction

The use of dental implants has revolutionized the treatment of partially and fully edentulous patients today. Implants have become a treatment approach for managing a broad range of clinical dilemmas due to their high level of predictability and their ability to be used for a wide variety of treatment options. While in many cases dental implants have been reported to achieve long-term success, they are not immune from complications associated with improper treatment planning, surgical and prosthetic execution, material failure, and maintenance. Included in the latter are the biologic complications of peri-implant mucositis and peri-implantitis, inflammatory conditions in the soft and hard tissues at dental implants. Peri-implant mucositis is characterized by inflammation in the mucosa around the implant without signs of bone loss. If bone loss also occurs, the condition is designated as peri-implantitis. Studies reported 43% and 22% prevalence of peri-implant mucositis and peri-implantitis, respectively. Peri-implant mucositis is a reversible condition, but if left untreated can progress to peri-implantitis. Besides mechanical treatment, other therapies have been used for treatment of peri-implant mucositis, namely: 1) triclosan-based dentifrice; 2) abrasive air blasting with sodium carbonate and resin curets; 3) mouth rinses with 0.2% chlorhexidine and 1% gel; 4) 0.5% chlorhexidine gel; and 5) irrigation with 0.12% chlorhexidine solution, as well as use of systemic antibiotics.

Stabilized chlorine dioxide exhibits antimicrobial properties against oral bacteria. Clinical and laboratory evidence suggest that stabilized chlorine dioxide oral rinse reduces the number of bacteria in the mouth, essentially eliminates oral malodor, reduces the signs of gum disease, and has bactericidal properties comparable to other products with additional consumer acceptability relating to its non-alcoholic and non-staining features. Thus, the purpose of this study was to analyze efficacy of stabilized chlorine dioxide mouth rinse as a chemical adjuvant for treatment of peri-implant mucositis in a non-surgical treatment protocol with a 3-month follow-up.

[2] Objective

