6. Study Duration and Visits: The study duration was (3 months) and was comprised of a total of 4 visits: Screening and hygienic phase therapy (weeks -2 to -1), Baseline (Visit 1, Day 0), Visit 2 (14 days), Visit 3 (45 days), Visit 4 (90 days).
7. Subjects received an Oral Hygiene Kit at Visit 1. The Modified Gingival Index (MGI), Bleeding on Probing (BOP) and Plaque Index (PI), Pocket depth and radiographs were measured, and all oral tissues examined (baseline examination). Subjects returned for Visit 2 in 14 days \pm 3 days to: 1) assess and record changes in indices and oral health and any adverse conditions. Visit 3 (45 days \pm 7) was a compliance visit for study drug utilization. Visit 4 (90 days \pm 7) was a repeat of Visit 1. Samples for microbiome analysis were collected at baseline (Visit 1), Day 14 (Visit 2), and Day 90 (Visit 4).
8. All parameters for clinical exam were calibrated between the examiners involved with the study.

[6] Study Materials (Oral Hygiene Kit)

STUDY DRUG

Both the active and placebo drugs were provided in liquid form, intended for oral administration. Sample products were labeled by the manufacturer and shipped directly to the site.

ADMINISTRATION

After tooth brushing in the morning and evening, the study product was administered orally using a cup that measures 15 mL of oral rinse, swishing in the oral cavity for 30 seconds and expectorating.

[7] Subjects

Subject recruitment occurred at the discretion of the Principal Investigator. After being recruited, potential subjects were informed of the purpose of the study and guided through HIPAA documentation and the informed consent process. Upon their understanding of the study, HIPAA regulations, and their agreement with the terms of the informed consent, subjects indicated so by signing the forms. The eligibility of potential subjects was determined through a series of screening interviews and an oral examination. Following screening, those potential subjects who retained eligibility were enrolled in the study at the discretion of the Principal Investigator. Approximately 75 subjects were screened to provide 54 enrollees. Once these subjects were randomized, study enrollment was complete.

Number of subjects: 54 subjects

Age: 18 years to 80 years

Gender: Both male and female subjects entered this study.

Remaining Natural Teeth: Minimum of 20

[8] Subject Eligibility Criteria

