Each subject was enrolled into the study based upon an initial interview and screening examination certifying the following conditions:

INCLUSION CRITERIA

Inclusion criteria included systemically healthy, partially edentulous patients rehabilitated with functional dental implants and prostheses for at least 1 year, at the Department of Periodontics Stony Brook University. All patients were selected from Stony Brook Dental Clinic and were detected with different peri-implant diagnoses.

Patients included had:

1. diagnosis of peri-implant mucositis;
2. at least at one implant;
3. minimum of 20 natural teeth
4. probing depth (PD) \leq 5mm;
5. BOP (bleeding on probing);
6. No radiographic evidence of bone loss beyond the first two threads of the implant.

EXCLUSION CRITERIA

1. Active Periodontitis or Peri-implantitis, which required definitive treatment.
2. Presence of oral local mechanical factors that could have (in the opinion of the PI) influenced the outcome of the study.
3. Presence of orthodontic appliances, or any removable appliances, that impinged on the tissues being assessed.
4. Presence of soft or hard tissue tumors of the oral cavity.
5. Patients treated with systemic antibiotic therapy or periodontal/mechanical/local delivery therapy within 12 weeks prior to study entry and throughout the study duration.
6. Patients chronically (i.e. two weeks or more) treated with non-steroidal anti-inflammatory drugs (NSAIDs) or any medications known to affect soft tissue condition (excluding treatment of Acetylsalicylic acid \leq 100 mg/day).
7. Patients with uncontrolled diabetes, of any type, and/or patients with HbA1c test value $>7.5\%$ dated 3 months prior to the screening visit.
8. Patients who were receiving radiation therapy to the head and neck area and/or receiving immunosuppressive therapy.
9. The presence of any medical or psychiatric condition or any other condition that, in the opinion of the Investigator, could have affected the successful participation of the patient in the study.
10. Drug and alcohol abuse.
11. Patients who were participants in any other clinical study 30 days prior to the start of the study and throughout the study duration.
12. Subject was pregnant (based on pregnancy result) or lactating.
13. Subject was a smoker or had been a smoker within the past 6 months.
14. Any other condition that may have interfered with the study as judged by the PI.

ASSIGNMENT

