- a) Gingival inflammation (MGI)

Secondary analyses were the comparison of data with respect to product effectiveness:

- a) Reduction in bleeding on probing (BOP) and Turesky modification of the Quigley-Hein Plaque Index (PI) grading on all natural teeth in the dentition

The primary statistical analytic framework was the repeated measures analysis of variance on three primary outcomes: probing depth, gingival index, and plaque. The primary hypothesis tested was the treatment by time interaction, i.e., did one treatment work better during the observations of these three outcomes? In other words, not just the total change, but also the rate of that change might differ between treatments. The proposed analysis was based on data that were generally normally distributed and similarly. If not, data transformations or link functions were used.

Outcomes

Raw data were collected from examinations of each tooth with regard to probing depth, gingival index, and plaque. Data were collected over three time periods, recorded into patient files, and transferred to Excel Workbooks, with one Workbook per patient. Each Workbook contained three tabs, one for each visit.

The raw data were combined as two levels of indexes for the three measures. The first outcome was a global score index of probing depth, gingival index, and plaque measurement. The global index was derived from individual tooth scores for each measure divided by the number of teeth measured. The second index derived from the same raw data described the three measures in terms of average scores for implant and non-implant teeth.

For the second analysis, implanted tooth data were separated from normal teeth data within each patient. Implant scores for each patient were averaged for probing depth, gingival index, and plaque scores. If a patient had one implant, each score was identical to the single measurement. With more than one implant, a single implant score for each patient was derived from averaging each of the three measures over the three observation periods. Likewise for each patient, the non-implanted teeth measures were averaged for each of the three times of assessment.

Individual patient data of the averages of the implant and non-implant teeth were calculated for each time period and transferred to a master data sheet.

Data Management and Statistical Analysis

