Transformed Variable: Average outcomes					
Source	Type III Sum of Squares	df	Mean Square	F	Sig.
Intercept	2790.339	1	2790.339	9371.807	0.000
Implant	2.916	1	2.916	9.793	0.002
Measure	13.625	1	13.625	45.761	0.000
Group	1.954	1	1.954	6.562	0.011
Implant * measure	7.58	1	7.58	25.459	0.000
Implant * group	0.018	1	0.018	0.061	0.805
Measure * group	8.331	1	8.331	27.981	0.000
Implant * measure * group	16.127	1	16.127	54.166	0.000
Error	60.738	204	0.298		

Implants and Probing depth

Probing depth scores (PDS) were only collected at initial and last observations visits 1 and 4. At intake, control group (Group A) patients had significantly higher levels of probing depth around implanted teeth (mean = 2.93, SEM = 0.094) than in non-implanted teeth (2.69, 0.063), with $t = 2.31$, $df = 53$, $p = 0.025$. In addition, control group (Group A) implant site probing depth was greater at intake than for test group (Group X) probing depth at implanted sites, 3.40 (0.109) versus 2.45 (0.080) respectively, with $t = 7.07$, $df = 52$, $p < 0.001$.

[figure not shown]
Table 5 represents the results in an overall test of significance with PDS as a dependent variable. There were two notable interactions. One was a time by group interaction, representing that probing depths changed significantly differently over time. Another was a three-way interaction time-by-implant-by-group assignment. The time-by-group interaction was seen before in the PDS score and while significant, the actual difference was less than 1%. The three-way interaction is a false signal in that implant scores probe scores increased slightly in the test group (Group X) and decreased slightly in the control group (Group A) – and neither change was significant.

Probing depth scores for implant and non-implant sites did not change significantly in both groups did not change significantly in both implant and non-implant sites as observed over time for both groups. Figure 8 illustrates the lack of change in implant and non-implant depth scores in either group.

Table 5. Summary results of general linear model of probing depth measures for implant sites over time.

Tests of Within-Subjects Contrasts					
Measure: GGI					
Source	Type III Sum of Squares	df	Mean Square	F	Sig.
Time	15.113	1	15.113	563.159	0.000
Time * implant	1.507	1	1.507	56.172	0.000
Time * group	0.941	1	0.941	35.047	0.000
Time * implant * group	0.001	1	0.001	0.041	0.840
Error(Time)	2.737	102	0.027		

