Figure 8. No differential effects of mouthwashes on probing depth between implant and non-implant sites. Both groups showed only slight decreases in probing depth. Note that in control condition (rinse A), probing depth was higher for the implant group at baseline.

Implants and Gingival Index

Implant versus normal oral sites also showed a significant main effect ($F = 79.0$, $df = 1$, $p < 0.001$) indicating more and faster gingival index improvement in test group (Group X) for both implant and non-implant sites. Test group (Group X) implants decreased in gingival index scores by 83% while implants in control group (Group A) decreased by 57%. The non-implant sites for control group (Group A) decreased by 23% and for test group (Group X) by 50%. The rate of change was faster for test group (Group X) implants than for control group (Group A) and faster than test group (Group X) non-implant sites. Test Treatment (rinse X) members' implants decrease in gingival index measured 26% versus 19% for those in control group (Group A).

[figure not shown]
Table 6 indicates a strong and statistically significant difference between implant and non-implant sites between and within groups – over time. Figure 9 illustrates the higher gingivitis index in test group (Group X) and greater and faster decrease of gingivitis in test group (Group X).

Table 6. Summary results of general linear model of gingival index measures.

Tests of Between-Subjects Effects

Gingivitis					
Source	Type III Sum of Squares	df	Mean Square	F	Sig.
Intercept	1207.001	1	1207.001	11073.258	0.000
implant	9.949	1	9.949	91.274	0.000
group	9.177	1	9.177	84.187	0.000
implant * group	8.613	1	8.613	79.021	0.000
Error	11.118	102	0.109		

Figure 9. Significant differential effects of mouthwashes on gingival index at implant sites. Both groups showed significant decreases in plaque, but the test group (Group X) reduced gingival index scores more and at a faster rate. Note the difference in gingival index scores at the beginning of the trial.

Implants and Plaque

Plaque scores (PS) for both implant and non-implant plaque scores were higher in the test group (Group X) (2.99 (0.071)) than in the control group (Group A) (2.35 (0.100)) at the first visit, $t = 5.45$, $df = 55$, $p < 0.001$. As with gingival index, PS decreased more for test group (Group X) patients (-0.799 (0.109)) than for control group (Group A) (-0.156 (0.064)) in both implant and non-implant sites, $t = 5.75$, $df = 55$, $p < 0.001$.

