There is a clear advantage to using ClōSYS® Ultra Sensitive oral rinse treatment (test rinse X) in terms of plaque and gingival index. In addition, ClōSYS® Ultra Sensitive oral rinse (test rinse X) appeared to have a preferential benefit for implant sites, over both control treatment (placebo rinse A) and over non-implant sites. The ClōSYS® Ultra Sensitive rinse (test rinse X) significantly reduced the plaque index and gingival index as compared to initial measures and those in control group (placebo rinse A) ($p < 0.001$). The observation of higher initial gingivitis scores for the ClōSYS® Ultra Sensitive oral rinse (test rinse X) did not affect the superiority of this test group treatment. In controlling for the inequality at baseline, and analysis of covariance showed the reduction of the plaque score remained significantly better in the ClōSYS® Ultra Sensitive oral rinse group (test rinse X) than for the control group (placebo rinse A) ($p < 0.001$). Also, using pre-post difference scores and slopes of the scores over time showed the treatment effect to be robust to the mismatch of initial levels of gingivitis and plaque ($P < 0.001$ for both).

Both groups improved from the use of mouthwashes, but the ClōSYS® Ultra Sensitive oral rinse (test rinse X) improved more and at a faster rate ($p < 0.001$) compared to the control group (placebo rinse A). There was no apparent effect on periodontitis between the two intervals in which it was measured.

Implant sites were significantly more ($p < 0.001$) and faster ($p < 0.001$) improved in the ClōSYS® Ultra Sensitive oral rinse group (test rinse X) than the other non-implanted teeth and in the control group (placebo rinse A).

Both ClōSYS® Ultra Sensitive oral rinse (test rinse X) and placebo rinse (rinse A) tested are safe to oral tissues and did not show any adverse effects.

Both ClōSYS® Ultra Sensitive oral rinse (test rinse X) and placebo rinse (rinse A) tested are safe to oral tissues and do not have any adverse effects.

Signature Page

[name]

Principal Investigator

[name] [name], PhD

REFERENCES

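### The conclusion on periodontitis rests on mean probing depth alone: Day 90 radiographs are not reported, and the implant probing-depth results contradict each other and are backed by a table labelled GGI

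*Combined protocol and SAP*

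**What the plan says.** All references are to the combined protocol and SAP.

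- **Disease background.** Section [1] separates mucositis from peri-implantitis by bone: "If bone loss also occurs, the condition is designated as peri-implantitis". It adds: "Peri-implant mucositis is a reversible condition, but if left untreated can progress to peri-implantitis".
- **Radiographs.** The schedule in section [4] puts X-rays at Baseline and Visit 4, and section [9] lists them at both visits. Of baseline, section [5] says: "Pocket depth and radiographs were measured, and all oral tissues examined (baseline examination". The only stated use of bone level is inclusion criterion 6 in section [8]: "No radiographic evidence of bone loss beyond the first two threads of the implant".
- **Analysis.** Section [11] analyses probing depth, gingival index and plaque. It names no radiographic or progression outcome, and the Results report none. Probing depth is a patient mean over all teeth, or separate means over implants and non-implanted teeth: "With more than one implant, a single implant score for each patient was derived from averaging each of the three measures". For a patient with one implant, the score is that implant's own value.
- **Implant probing depth.** The Implants and Probing depth section names a three-way interaction (time, implant, group) as notable. It then calls it a false signal because "implant scores probe scores increased slightly in the test group (Group X) and decreased slightly in the control group (Group A"), with neither change significant. The Figure 8 caption says: "Both groups showed only slight decreases in probing depth".
- **Conclusion.** "There was no apparent effect on periodontitis between the two intervals in which it was measured"

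**The concern.** The concluding sentence names a disease that the trial did not measure as an outcome. A reader could take it as saying that deeper disease was looked for and not found. What was tested is a difference in mean probing depth. The scheduled assessment that bears on bone, the Day 90 film, goes unreported.

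The same Conclusions claim a preferential benefit at implant sites and safety to oral tissues. Implant probing depth is the one reported measure of deeper tissue at those sites, and from this document a reader cannot tell which way it moved in the test arm, by how much, or whether the arms differed. The argument for setting the interaction aside is also unsound: two non-significant within-arm changes do not test the contrast between arms.

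**Working it through.** **1. The test behind the conclusion.** Table 2, slope of global probing depth: group SS 0.125 on 1 df, error SS 5.75 on 55 df.

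F = 0.125 / (5.75/55) = 1.196, p = 0.279. The stated F = 1.191, p = 0.28 agrees within rounding.

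This test concerns the mean over all teeth, not implants and not bone. Its precision can be recovered approximately. The Global Probing Depths section gives 2.76 to 2.64 in control (fall 0.12) and 2.68 to 2.37 in test (fall 0.31), a difference in change of 0.19 mm. The mean slope is half the mean change (-0.213/2 = -0.106), so both share one t:

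- t = √1.191 = 1.091
- SE = 0.19/1.091 = 0.174
- 95% CI = 0.19 ± 2.004 × 0.174 = -0.16 to 0.54 mm (positive means a larger fall in test)

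So a difference was not shown; it was not excluded. One caution: Table 3 lists a minimum of 0 for global probing depth at time 3. A patient mean of 0 mm is implausible and may be a missing visit entered as zero, which only the raw data can settle.

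**2. Final-visit p value.** From the stated SEMs, t = (2.64 - 2.37)/√(0.130² + 0.166²) = 0.27/0.211 = 1.28, close to the stated 1.27. On 55 df, t = 1.27 gives two-sided p = 0.21, not 0.28. The printed 0.28 equals the slope-test p in Table 2 and may have been carried over.

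**3. Table 5.** The title says probing depth; the measure label inside says GGI. Error MS = 2.737/102 = 0.0268.

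| Term | F recomputed | F stated | p stated |
|---|---|---|---|
| Time | 15.113/0.0268 = 563.2 | 563.159 | 0.000 |
| Time × group | 0.941/0.0268 = 35.1 | 35.047 | 0.000 |
| Time × implant × group | 0.001/0.0268 = 0.037 | 0.041 | 0.840 |

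The table is consistent with itself (the last row differs only through the rounded SS) but not with the text. A Time F of 563 cannot sit beside a statement that probing depth did not change significantly. With p = 0.840 there is no three-way interaction in the table to dismiss. No implant probing-depth model, and no Day 90 implant depth by arm, is shown anywhere.

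**4. Text against text.**

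| Point | One place | Another place |
|---|---|---|
| Direction at implants | Implants and Probing depth: up in test, down in control | Figure 8 caption: decreases in both groups |
| Treatment-by-time interaction | Global Probing Depths: none | Implants and Probing depth: seen before, and significant |
| Control implant baseline | 2.93 (0.094) | 3.40 (0.109), also in Table 1 |

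On the last row, the mean pooled over both arms is (27 × 3.40 + 26 × 2.447)/53 = 2.93. The 2.93 therefore looks like a pooled value labelled as control.

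**5. What counts could show.** With zero events in n patients, the upper limit is 1 - α^(1/n) with α = 0.05 (one-sided) or 0.025 (two-sided 95%):

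- n = 26: 10.9% one-sided, 13.2% two-sided
- n = 29: 9.8% one-sided, 11.9% two-sided

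Both n are needed because the Patients section gives 26 test patients while its breakdown sums to 18 + 9 + 2 = 29. For power, assume 27 per arm, two-sided 0.05 and illustrative rates: about 10% for 5% vs 10%, and 54% for 5% vs 25%.

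**The case against.** - **A reader might infer that a progression endpoint was dropped.** The documents do not support this. Progression is not an objective, endpoint or hypothesis, and no purpose is given for the X-rays. The Day 0 film may have served eligibility. Section [1] ties progression to untreated mucositis, and both arms received basic therapy. This is an unreported assessment.
- **A reader might infer that the rinse worsened implants.** The documents do not support this either. The rise has no stated size and is called non-significant. Baseline implant depth was 3.40 in control and 2.45 in test, so a small rise in test and fall in control is compatible with regression to the mean.
- **Averaging does not hide everything.** The Patients section gives 29 of 56 patients (52%) with a single implant, and their implant score is undiluted. Dilution affects patients with several implants, the whole-mouth score and arm means.
- **The sentence may be loose wording.** The Results elsewhere describe the global index in periodontal-disease terms, and a measure taken twice fits probing depth. That is the likeliest reading, and it still requires the sentence to be corrected.
- **The Figure 8 caption may refer to all sites together.** A small implant rise could then coexist with it. But it captions the implant versus non-implant comparison, and the figure is not available to settle the matter.

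What stands after these points: the conclusion exceeds its evidence, the film result is absent, and the implant probing-depth account cannot be followed. None of the objections explains Table 5.

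**Conclusion.** The point holds as one of reporting and interpretation. The data support only this: no statistically significant between-arm difference in change in mean global probing depth was shown (p = 0.28), with an approximate 95% CI of -0.16 to 0.54 mm reconstructed from rounded summaries. They say nothing about bone, peri-implantitis or periodontitis as a diagnosis.

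For implants, the documents establish neither the direction nor the size of change in the test arm, because the supporting table is labelled with another measure and disagrees with the text. Neither a progression rate nor the size of the rise can be computed from what is given. The statement that no radiographic outcome exists rests on section [11] and the Results as published.

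**What to change.** 1. **Reword the conclusion** along these lines: *no statistically significant between-arm difference in change in mean global probing depth was shown; radiographic progression was not analysed*. A bare statement of no difference would again read a non-significant test as absence of effect.
2. **Replace Table 5** with the actual implant probing-depth model. Give implant probing depth by arm at both visits, with the baseline-adjusted between-arm difference and 95% CI. Reconcile the Global Probing Depths section, the Implants and Probing depth section and the Figure 8 caption. Correct the 2.93/3.40 baseline and the final-visit p value, and check the zero minimum in Table 3 against the raw data first.
3. **Add descriptive counts from data already recorded.** By arm, give the number of implants and patients with probing depth above the 5 mm entry limit at Day 90. Where paired films are usable, add a reading by the existing examiners of bone loss beyond the first two threads. The films should be coded and read masked, because the label key has been released. Give denominators and exact limits, and settle the test-arm n (26 or 29) first.

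Items 1 and 2 need only rewording and a re-run on existing data. Item 3 needs some extra reading time and depends on the films covering the implants comparably at both visits, which the documents do not state. The counts would be descriptive only. The cost beyond that is a less favourable conclusion.
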